13.2 Sample Size, Accrual Rate and Study Duration

Based on data of recent trials in a similar population of patients with metastatic breast cancer treated with sacituzumab govitecan, a median PFS of 5.5 months would be expected with sacituzumab govitecan monotherapy.³² Currently, there are no published data about the PFS of patients with HR+ / HER2- MBC treated with sacituzumab govitecan in combination with anti-PD-1 therapy. We anticipate that achieving a PFS of at least 8.5 months for combination therapy (Arm A) in the present study would make the regimen worthy of further investigation. Considering a one-sided 0.1 type-I error and 80% power to detect a 3-month absolute difference in median PFS at the time of final analysis (hazard ratio = 0.65), 110 patients would need to be enrolled on the trial.

The final analysis will occur when 100 PFS events are observed, or 2 months after the last patient is randomized, whichever occurs first. An interim analysis for futility will occur when $\sim 50\%$ of the information is obtained (50 PFS events). The study would stop early if the Z-statistic from a log-rank test is less than 0. It is estimated that the interim analysis will occur approximately 18 months after the first patient is randomized.

The expected accrual rate is 4-5 patients per month, with accrual of 110 patients anticipated to be completed at 24 months. The expected study duration to primary analysis of PFS is 2.5 to 3 years.

13.2.1 Change in timing of the final analysis

At the time of the October 2023 DSMB reporting, it became clear that 100 PFS events would not be reached in this study (due to higher rates of treatment discontinuation for reasons other than progression than expected) and so the final PFS analysis would only occur 9 months after the last patient was randomized. This would result in a longer study timeline than expected (45 months since accrual was completed at 36 months). Changing the final analysis from 9 months after the last patient is randomized to 2 months after the last patient is randomized (i.e., 38-month study duration to primary PFS analysis) would result in approximately 5% decrease in study power. Given the treatment landscape and emerging data for TROP2 antibody drug conjugates for metastatic HR-positive/HER2-negative breast cancer, this relatively small loss of power was considered acceptable against the alternative of waiting to report the results and, hence, the final analysis will now be conducted 2 months after the last patient is randomized.

13.3 Stratification Factors

There are no planned stratification factors for this trial.

13.4 Interim Monitoring Plan

We will perform a safety run-in analysis in the first 12 patients randomized to the combination therapy arm. If there are 4 or more dose-limiting toxicity (DLTs) in the first 12 patients included, enrollment will be halted to discuss whether the study will be amended, with re-evaluation of the appropriate dosing schedule and study design or closed. The probability of observing 4 or more DLTs in the first 12 if the true DLT rate is 15% or lower is less than 10%. The probability of observing 4 or more DLTs in the first 12 if the true DLT rate is 30% or higher is greater than 50%. Section 5.4 describes the DLT definitions used in this current study, which will be assessed in the first cycle (21 days). In the case that enrollment continues, these first 12 patients will be included in the efficacy analysis.

An additional interim analysis for futility will occur when ~50% of the information is obtained (after 50 PFS events have occurred). The study would stop early if the Z-statistic from a log-rank test is less than 0.

13.5 Analysis of Primary Endpoints

The primary objective is to compare the median PFS achieved with the experimental combination of sacituzumab govitecan plus pembrolizumab versus sacituzumab govitecan alone, and this will be assessed among all patients who initiated protocol therapy according to the randomized treatment assignment.

PFS is defined as the time from study randomization to disease progression, according to RECIST 1.1 or medical judgment, the latter based on established clinical parameters, such as rising tumor markers and physical exam evidence of progression, i.e., worsening chest wall disease, or death due to any cause, whichever occurred first. Patients alive without disease progression are censored at the date of last disease evaluation. Definitive analysis of the efficacy data will be based on the modified intent-to-treat principle where all patients who initiate protocol therapy will be analyzed as randomized.

The Kaplan-Meier estimates will also be calculated separately for patients allocated to each treatment regimen. Multivariable Cox proportional hazards models will be used to estimate treatment efficacy in PFS with adjusting for potential confounders such as age at study entry, stage (locally advanced or metastatic), visceral metastases (yes or no), level of ER expression (1-9% vs. 10% or greater), and rapid recurrence after completion of adjuvant therapy < 6 months (yes or no). Potential interactions between treatment and clinical factors will be explored in the Cox models. Model diagnostics will be performed to check whether the proportionality assumption is valid in those models. Should it fail, appropriate analysis, such as models with time-dependent effects, will be explored. An exploratory subset analysis in the eligible-only population will also be performed, and results of this analysis will be compared with those from the intent-to-treat population in the primary analysis. Any substantial difference will be carefully examined.

13.6 Analysis of Secondary Endpoints

Efficacy Endpoints

- Among patients who initiated protocol therapy and whose tumor was centrally confirmed to be PD-L1-positive (as defined by CPS ≥ 1 using the PharmDx 22C3 assay), the efficacy, as assessed by PFS, of sacituzumab govitecan plus pembrolizumab will be compared to sacituzumab govitecan alone. PD-L1 status will be defined by central confirmation of PD-L1 testing on the baseline research biopsy, if available; if not available, then the central PD-L1 testing results from the archival sample will be used. The comparison of PFS between treatment arms in the PD-L1-positive subgroup will be exploratory.
- In the modified ITT and PD-L1-positive population, all patients who initiated protocol therapy will also be evaluated for ORR (according to RECIST 1.1), CBR, DOR, TTOR and OS.

Radiographic response will be assessed using RECIST 1.1 criteria, as defined in section 11. Objective response will require confirmatory scans or exam as indicated. The ORR (CR + PR), according to RECIST 1.1, will be reported with 95% confidence intervals. Clinical benefit is defined as CR, PR or SD ≥ 24 weeks according to RECIST 1.1 and will be reported with 95% confidence intervals. Median DOR and TTOR will be reported with ranges. Overall survival, defined as the time from randomization (or registration) to death due to any cause with censoring at date last known alive, will be reported with Kaplan Meier estimates.

For OS, the log-rank test will be one-sided. Treatment efficacy in these secondary endpoints will be assessed by Cox models adjusting for clinical factors such as age at study entry, stage (locally advanced or metastatic), visceral metastases (yes or no), level of ER expression (1-9% vs. 10% or greater), and rapid recurrence after completion of adjuvant therapy < 6 months (yes or no). Dichotomous endpoints of response will be compared using Cochran-Maentel-Haenszel chi-squared tests.

Safety and tolerability

All patients will be evaluable for toxicity from the time of their first treatment with any study agent. Toxicity will be graded according to NCI CTCAE, Version 5.0. Toxicities will be summarized by maximum grade and by treatment arm. Incidence rate of each toxicity will be reported with 95% confidence intervals. The incidence rates of any grade 3 or higher toxicity will be compared across arms using a two-sided Fisher's exact test.

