1.3 Secondary Objectives

- To compare the PFS of sacituzumab govitecan with pembrolizumab to that of sacituzumab govitecan alone in the subgroup of patients with PD-L1-positive HR+ / HER2- MBC.
- To compare the efficacy of sacituzumab govitecan with pembrolizumab to that of sacituzumab govitecan alone by assessing other clinical outcome measures, including overall survival (OS), objective response rate (ORR) by RECIST 1.1, duration of response (DOR), time to objective response (TTOR), time to progression (TTP), and clinical benefit rate (CBR), in all-comers (regardless of PD-L1 status) and in the subgroup of patients with PD-L1-positive HR+ / HER2- MBC.
- To evaluate the safety and tolerability of sacituzumab govitecan and pembrolizumab compared to sacituzumab govitecan alone by monitoring adverse events, including immune-related adverse events.

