11.1.4 Duration of Response

Duration of overall response: The duration of overall response is measured from the time measurement criteria are met for CR or PR (whichever is first recorded) until the first date that recurrent or progressive disease is objectively documented (taking as reference for progressive disease the smallest measurements recorded since the treatment started, or death due to any cause. Participants without events reported are censored at the last disease evaluation).

Duration of overall complete response: The duration of overall CR is measured from the time measurement criteria are first met for CR until the first date that progressive disease is objectively documented, or death due to any cause. Participants without events reported are censored at the last disease evaluation.

Duration of stable disease: Stable disease is measured from the start of the treatment until the criteria for progression are met, taking as reference the smallest measurements recorded since the treatment started, including the baseline measurements.

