11.1.5 Time to Response

Time to objective response: The time to objective response is defined as the time from randomization to the date of the first documented CR or PR (whichever is first recorded).

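### The planned Cox comparison of duration of response can use responders only, so its hazard ratio is not a randomized comparison; DOR should be descriptive, by Kaplan-Meier

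*Combined protocol and SAP*

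**What the plan says.** Section 1.3 puts DOR and time to objective response (TTOR) among the outcomes on which the two regimens are to be compared. Section 13.6 says that, in the modified ITT and PD-L1-positive populations, "all patients who initiated protocol therapy will also be evaluated for ORR (according to RECIST 1.1), CBR, DOR, TTOR and OS". It then says that "Treatment efficacy in these secondary endpoints will be assessed by Cox models adjusting for clinical factors", with five factors given as examples: age, stage, visceral metastases, ER level and rapid recurrence. The following sentence sends dichotomous response endpoints to Cochran-Mantel-Haenszel tests. No list says which endpoints the Cox models cover, or in which patients.

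For summaries, Section 13.6 says "Median DOR and TTOR will be reported with ranges", with no estimator and no confidence interval. OS "will be reported with Kaplan Meier estimates", and Section 13.5 names Kaplan-Meier for PFS.

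The definitions are in Section 11.1. For DOR (11.1.4): "The duration of overall response is measured from the time measurement criteria are met for CR or PR", and "Participants without events reported are censored at the last disease evaluation". TTOR (11.1.5) is the "time from randomization to the date of the first documented CR or PR", with no rule for patients who never respond.

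Section 13.6 labels the PD-L1-positive PFS comparison exploratory. DOR carries no such label.

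**The concern.** Once the dichotomous endpoints go to Cochran-Mantel-Haenszel tests, OS, DOR and TTOR are left for the Cox sentence. For DOR, the model compares the responders of Arm A with the responders of Arm B. Treatment itself decides who enters each group, so randomization no longer makes the groups comparable. If pembrolizumab turns some non-responders into short-lived responders, Arm A's DOR looks worse although nobody has been harmed. If the extra responses are unusually durable, the contrast mixes that selection with any effect on duration. The baseline covariates can balance only what they measure. The stake is that an adjusted DOR hazard ratio could be published as treatment efficacy with the plan's authority behind it.

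A second, smaller matter is that DOR is a censored time and the cut-off has been moved earlier (Section 13.2.1), yet the plan does not say how the median is to be estimated.

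**Working it through.** **Plan figures that can be checked.** The documents give no responder count, power or censoring figure for DOR. The PFS design figures do reproduce:

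- Events = 4(1.2816 + 0.8416)² / (ln 0.65)² = 4 × 4.508 / 0.1856 = 97.2, so 98. Power at 100 events is 0.809. The plan says 100 events and 80%.
- With 36-month uniform accrual and exponential PFS medians of 5.5 and 8.5 months, expected events are 97.6 at +9 months (power 0.801) and 85.6 at +2 months (power 0.762). That is about 4 points, or 5% relative, in line with the loss stated in Section 13.2.1. The same accrual and cut-off are used below.

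**Inputs for DOR.**

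- 110 patients (13.1).
- ORR 31.5% in the HR+/HER2- cohort (2.4.5).
- Time to response 2 months and median DOR 7.7 months, both from the TNBC cohort (2.4.5) and used here as a proxy.
- Accrual 36 months, cut at 38 months (13.2.1). The documents set this cut for PFS; applying it to DOR is an assumption.
- Exponential DOR (assumed).

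**Responders.** 110 × 0.315 = 34.7, about 35, or about 17 per arm.

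**Administrative censoring.** A patient entering at time e and responding 2 months later is followed for 38 − e − 2 = 36 − e months after response, which is uniform on 0 to 36. With λ = ln 2 / median, the censored fraction is (1 − e^(−36λ)) / (36λ).

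| Median DOR (months) | 36λ | Censored |
|---|---|---|
| 5.5 | 4.54 | 22% |
| 7.7 | 3.24 | 30% |
| 8.5 | 2.94 | 32% |
| 10 | 2.50 | 37% |
| 12 | 2.08 | 42% |

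An added loss to assessment (assumed exponential, median 24 months) gives 42% at 7.7 months and 33-54% across the table. Some such loss is to be expected, because Section 5.8 stops tumor assessments when another anti-cancer therapy starts.

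**Events and model size.** 34.7 × 0.70 = about 24 events. Treatment plus the five listed covariates, one term each, is 6 parameters: 24 / 6 = 4 events per parameter. Even without covariates, SE(log HR) ≈ 2/√24 = 0.41, so a 95% interval spans a factor of e^(1.96 × 0.41) ≈ 2.2 either way. Power for HR 0.65 at one-sided 0.1 is Φ(0.431 × √24 / 2 − 1.282) = Φ(−0.23) = 0.41. In PD-L1-positive patients (20-25% by Section 2.5, so 22-28 patients), 0.315 × 22 to 27.5 gives about 7-9 responders in both arms together.

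**Illustration of selection (assumed).** Suppose Arm A keeps its 31.5% of responders at a median of 7.7 months and gains 10 to 20 points of extra responders with a median of 3.9 months. For exponential times, the average rate ratio A/B over complete follow-up is 7.7 divided by the weighted mean of the medians.

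- 10 points: weights 0.759 and 0.241; 7.7 / 6.78 = 1.13.
- 20 points: weights 0.612 and 0.388; 7.7 / 6.22 = 1.24.

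No patient is worse off, yet DOR appears 13-24% worse in hazard. Long-lasting extra responses would reverse the sign.

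**Median DOR under two estimators.** If ongoing responses are treated as finished, the median t solves e^(−λt)(1 − t/36) = 0.5. At 7.7 months t is about 5.8, and 1 − 5.8/7.7 = 25% too low. In simulation with 17 responders per arm, the Kaplan-Meier median centres on about 7.75 months.

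**The case against.** The best reply is that this is loose drafting. The Cox sentence directly follows the OS log-rank sentence, DOR is reached by elimination, and no decision rule, alpha or power depends on DOR in this phase II trial. All of that is fair, and it limits the weight of the point. It does not remove it: the wording is plural, DOR stands in the list just above it, and Section 1.3 names DOR as an outcome to compare. That Section 13.6 evaluates DOR among all treated patients does not help, because Section 11.1.4 gives a non-responder no DOR value.

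Four stronger readings are tempting and are not supported:

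- **That TTOR has the same flaw.** TTOR starts at randomization, so a model in all treated patients is possible. What is missing is a rule for non-responders.
- **That DOR will be summarised by a naive median and so will be biased.** No estimator is named, and the censoring rule in Section 11.1.4 fits Kaplan-Meier. The 25% shortfall arises only if that rule is ignored.
- **That 30% censoring is a feature of the plan.** It appears nowhere in the documents. It rests on a TNBC-cohort duration and on a cut-off stated for PFS.
- **That the hazard ratio will be biased against Arm A by a known amount.** The 1.13-1.24 is a crude rate ratio under invented inputs, not the planned adjusted model, and it is small beside an interval spanning a factor of about 2.2.

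**Conclusion.** The point holds for DOR. On the natural reading, the plan calls for an adjusted between-arm Cox comparison in a subset defined after randomization, presents it as treatment efficacy, and attaches no caveat. That conclusion follows from the definitions and needs no assumed figure.

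The size is conditional: about 35 responders and 24 events, or 4 per parameter, given ORR 31.5%, median DOR 7.7 months, a 38-month cut and six parameters. Heavier censoring lowers the event count further (42% leaves about 20). The direction and size of any selection bias cannot be known in advance.

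The unnamed DOR estimator and the missing TTOR rule are gaps in detail, not demonstrated errors; alone they would be minor. The change should be made, but it concerns a secondary endpoint and leaves the primary PFS comparison untouched.

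**What to change.** Amend Section 13.6 as follows.

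1. **Cox models.** Name the endpoints covered, OS and TTP, and state that DOR is excluded. TTP is a secondary endpoint in Section 13.1 but is absent from the evaluation list in Section 13.6, so naming it also gives it a method.
2. **DOR.** Report it in responders, by arm, as a Kaplan-Meier median with 95% CI, using the censoring rule of Section 11.1.4. Label it descriptive, with no between-arm test or hazard ratio.
3. **If duration is to be compared.** Use a measure defined in all treated patients with non-responders at zero, such as mean time in response up to a fixed horizon. Set the horizon in advance, within the follow-up that the cut-off supports.
4. **TTOR.** State the analysis set: either descriptive in responders, or cumulative incidence of response in all treated patients with progression and death as competing events.

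The cost is a change of wording. No new data are needed. The sponsor gives up an adjusted DOR hazard ratio that would rest on about 24 events and could not be read as a treatment effect.

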1 OBJECTIVES

1.1 Study Design

This is a randomized phase 2 open label study of sacituzumab govitecan +/- pembrolizumab for patients with hormone receptor-positive (HR+) / HER2- metastatic breast cancer (MBC). Patients will be randomized in a 1:1 ratio to sacituzumab govitecan (IMMU-132) with pembrolizumab (Arm A) or sacituzumab govitecan alone (Arm B) and will be treated until unacceptable toxicity or progression as defined by RECIST 1.1 criteria.

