6.2 Management of Toxicities Attributable to Pembrolizumab

AEs associated with pembrolizumab exposure may represent an immunologic etiology. These immune-related AEs (irAEs) may occur shortly after the first dose or several months after the last dose of pembrolizumab treatment and may affect more than one body system simultaneously. Therefore, early recognition and initiation of treatment is critical to reduce complications. Based on existing clinical study data, most irAEs were reversible and could be managed with interruptions of pembrolizumab, administration of corticosteroids and/or other supportive care. For suspected irAEs, ensure adequate evaluation to confirm etiology or exclude other causes. Additional procedures or tests such as bronchoscopy, endoscopy, skin biopsy may be included as part of the evaluation.

Based on the severity of irAEs, withhold or permanently discontinue pembrolizumab and administer corticosteroids. Dose modification and toxicity management guidelines for irAEs associated with pembrolizumab are provided in Table 4.

Key dose modification management steps to highlight include:

- Permanently discontinue pembrolizumab for recurrent grade 2 pneumonitis.
- Permanently discontinue pembrolizumab for any instance of myocarditis, regardless of grade.

Subjects receiving corticosteroids for treatment of drug-related adverse events must be at \leq 10 mg/day prednisone or equivalent prior to re-initiation of pembrolizumab.

Table 4. Dose modification and toxicity management guidelines for immune-related AEs associated with pembrolizumab

General instructions:				
irAEs	Toxicity grade (CTCAE V5.0)	Action with pembrolizumab	Corticosteroid and/or other therapies	Monitoring and follow-up
Pneumonitis	Grade 2	Withhold	
• Administer corticosteroids (initial dose of 1 - 2 mg/kg prednisone or equivalent) followed by taper	
• Monitor participants for signs and symptoms of pneumonitis• Evaluate participants with suspected pneumonitis with radiographic imaging and initiate corticosteroid treatment
	Grade 3 or 4, or recurrent Grade 2	Permanently discontinue		

			
 • Add prophylactic antibiotics for opportunistic infections 	

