13.8.2 Evaluation of Safety

The safety population will be used in the safety data summaries. The safety population consists of all patients who took at least one dose of sacituzumab govitecan or pembrolizumab on study and who have at least one post-baseline safety assessment. Note that a patient who had no adverse events constitutes a safety assessment. Patients who have received at least one dose of study drug but have no post-treatment safety data of any kind will be excluded. Evaluation of safety analyses will use treatments as treated rather than as planned.

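### Toxicity is compared between arms only as crude proportions, with no account of time at risk, although the design implies longer treatment and a longer adverse-event window in Arm A

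*Combined protocol and SAP*

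**What the plan says.** Section 13.6 (Safety and tolerability) plans three things. The first is a severity table: "Toxicities will be summarized by maximum grade and by treatment arm". The second is an estimate: "Incidence rate of each toxicity will be reported with 95% confidence intervals". The third is a test: "The incidence rates of any grade 3 or higher toxicity will be compared across arms using a two-sided Fisher's exact test". Because the test is Fisher's, the incidence rate must be a proportion of patients and not a rate per unit of time. Section 13.8.2 adds only the analysis population: "Evaluation of safety analyses will use treatments as treated rather than as planned".

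No section plans a summary of treatment duration, an exposure-adjusted rate, a time-to-first-event analysis or a fixed-window comparison between arms. The 21-day dose-limiting-toxicity window in Sections 5.4 and 13.4 covers only the first 12 Arm A patients.

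On duration, Section 1.1 says that patients "will be treated until unacceptable toxicity or progression as defined by RECIST 1.1 criteria". On timing, Section 13.2.1 says that "the final analysis will now be conducted 2 months after the last patient is randomized". On collection after treatment, Section 7.2 sets the serious-event window at 30 days after the last dose, or 90 days for pembrolizumab. Section 5.8 and note p of the Section 10 calendar add a 90-day adverse-event assessment for patients given pembrolizumab.

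**The concern.** Section 1.3 makes safety a comparative objective and names immune-related events. A crude proportion depends on both the rate of toxicity and the time over which a patient is observed. Treatment runs to progression, so if the combination prolongs PFS, Arm A is observed on treatment for longer. It would then show more toxicity even if the monthly rate were the same in both arms. The reverse can also happen: if Arm A stops early for toxicity, the crude proportion understates its rate while on drug.

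Two features add to this. Adverse events are collected for longer after the last dose in Arm A. In addition, Section 6.2 says that immune-related events "may occur shortly after the first dose or several months after the last dose of pembrolizumab treatment", so a safety cut taken soon after the last randomization would miss some of them. The efficacy endpoints handle unequal follow-up by censoring, whereas the safety endpoint does nothing about it. A reader of the planned table could not tell toxicity added by pembrolizumab from toxicity due to longer treatment.

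**Working it through.** **The plan's own figure.** With 100 events, hazard ratio 0.65 and one-sided alpha 0.10, power = Φ(√100/2 × |ln 0.65| − 1.2816) = Φ(2.154 − 1.282) = 0.81. This agrees with the stated 80%. In the exposure model below, with no non-progression stopping, moving the cut-off from 9 to 2 months after the last randomization lowers power from 80.1% to 76.2%. That 3.9-point loss is in line with the roughly 5% given in Section 13.2.1, so the model is a fair reading of the design.

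**Inputs from the documents.** Median PFS is 8.5 and 5.5 months, with 55 patients per arm. Accrual took 36 months and the cut-off is 2 months later (Sections 13.1, 13.2 and 13.2.1).

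**Assumptions.** Times are exponential and accrual is uniform. Non-progression stopping has rate c per month, equal in both arms. Section 13.2.1 reports more such stopping than expected but gives no figure, so c runs from 0 to 0.08.

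**Exposure at cut-off.** The progression rate is μ = ln 2/median, which is 0.0815 (A) and 0.1260 (B) per month. With m = μ + c, mean exposure is the average of (1 − e^(−mu))/m over follow-up u, uniform from 2 to 38 months. The proportion still on treatment is the average of e^(−mu).

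| c per month | Mean months, A vs B | Ratio | Still on treatment, A vs B | Patients of 110 |
|---|---|---|---|---|
| 0 | 8.90 vs 6.59 | 1.35 | 27% vs 17% | 24 |
| 0.04 | 6.77 vs 5.30 | 1.28 | 18% vs 12% | 16 |
| 0.08 | 5.42 vs 4.42 | 1.23 | 12% vs 9% | 12 |

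**Crude incidence with the same hazard in both arms (c = 0).** Let p be the Arm B proportion with complete follow-up, and h = p/(1 − p) × μ_B. Incidence at cut-off is the average over u of h/(h + μ) × (1 − e^(−(h+μ)u)). For p = 10%, 30% and 75%, h is 0.0140, 0.0540 and 0.378 per month. The 75% case matches the proportion of sacituzumab govitecan patients with a grade 3 or higher event in Section 7.1.2.

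| p | Arm B | Arm A | Gap (points) |
|---|---|---|---|
| 10% | 8.5% | 11.2% | 2.7 |
| 30% | 26.8% | 33.7% | 6.9 |
| 75% | 73.5% | 80.3% | 6.8 |

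Dividing each proportion by mean months at risk to first event recovers h in both arms. For p = 75% this is 0.735/1.944 = 0.378 (B) and 0.803/2.123 = 0.378 (A), a rate ratio of 1.00.

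**Effect on the test.** Fixing Arm B at 10%, 30%, 50% and 75% at the cut-off gives Arm A 13.2%, 37.4%, 58.7% and 81.5%. Fisher's test at two-sided 0.05 (assumed, as the plan gives no level) rejects in 4%, 9%, 10% and 9% of trials. Its actual size is 2% to 3%.

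**If all the risk lies in the first 21 days**, the pairs are 30% vs 30.4% and 75% vs 75.9%.

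**Post-treatment window.** With equal PFS and a constant rate, collecting for 90 days in Arm A and 30 days in Arm B by itself turns 30% into about 36%. If safety is cut at month 38 and c = 0, about 35% of Arm A (19 of 55) would not have completed 90 days after the last dose. With c = 0.04 to 0.08, this is 14 to 11 of 55.

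**Cumulative incidence as an alternative.** With the end of treatment as a competing event, the 6-month value is h/(h + μ) × (1 − e^(−6(h+μ))). For p = 75% this gives 71.4% (B) and 77.0% (A), so 5.6 of the 6.8 points remain.

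**The case against.** The strongest reply is that crude incidence per arm is the right description of total harm under a policy of treating to progression, and this is a descriptive secondary endpoint in a 110-patient phase II trial. That stands, and it is why the table should be kept.

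Other parts of the reply also stand. Constant hazard is the unfavourable case: Section 6.3 provides for dose reduction after severe toxicity without re-escalation, so later risk may be lower. The exposure imbalance needs a PFS difference and largely disappears without one.

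Several stronger readings are tempting, but the documents do not support them:

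- A reader might infer that Arm A is treated 1.5 times as long. The ratio 8.5/5.5 = 1.55 compares median PFS, not treatment duration. Section 5.7 lists several other reasons for stopping.
- A reader might infer that many patients are still on treatment at the cut-off. No such count is stated, and the 24 of 110 above is a ceiling at c = 0.
- A reader might infer that the 19 incompletely followed Arm A patients are all counted as event-free. For the 75% event only 3.5% of Arm A (about 2 of 55) are both incompletely followed and event-free. The issue matters more for uncommon events: about 30% of Arm A in the 10% case.
- A reader might infer that late immune-related events will be under-reported. Section 13.2.1 moves the PFS analysis and no section fixes the safety cut at month 38. Adverse-event follow-up continues under Section 5.8.

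None of this supplies the missing account of time at risk.

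**Conclusion.** The point holds as a modest, inexpensive improvement. The planned comparison mixes the rate of toxicity with time on treatment, and nothing else in the plan allows the two to be separated.

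Under the design's own PFS assumption, the exposure ratio at month 38 is at most about 1.35, and 1.23 to 1.28 with the assumed extra stopping. The spurious excess in Arm A is about 3 to 7 points at equal constant hazards. It is close to nil for first-cycle toxicity and nil when exposure is equal. The unequal post-treatment window is a separate source of difference and remains even with equal PFS. Incomplete follow-up matters mainly for uncommon or late immune-related events, and only if safety is cut at month 38.

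These sizes rest on exponential times, uniform accrual, an assumed stopping rate equal in both arms, and constant hazard while on treatment. They do not show that the crude table is wrong or should be replaced.

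**What to change.** Keep the crude table and Fisher's test in Section 13.6, labelled as total harm per treatment strategy. Add:

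1. Treatment duration by drug and arm.
2. Rates of first grade 3 or higher event and first immune-related event per patient-month at risk, by arm, with 95% confidence intervals and a rate ratio. Time at risk runs from first dose to the first such event, the end of the common window, death or the data cut, whichever comes first.
3. A common post-treatment ascertainment window for the between-arm comparison, for example the 30 days that both arms share, with later Arm A events listed separately.
4. A stated safety data cut, and one refresh of the tables after the last Arm A patient has passed the 90-day assessment that Section 5.8 already requires.

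Cumulative incidence at 3 and 6 months with competing events may be added to handle patients still under observation. It does not remove the effect of longer treatment, so it should not be the main addition.

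The cost is SAP wording, modest programming from dosing and event-onset dates, a few table columns and one later update. That update may come late if an Arm A patient stays on treatment for a long time. The rates are easy to interpret only if the hazard is roughly constant, and the text should say so. No treatment rule or visit changes.
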